## List of Abbreviations

AD	Atopic Dermatitis
ADR	Adverse Drug Reaction
AE	Adverse Event
AESI	Adverse Event of Special Interest
ALT	Alanine Aminotransferase
ANC	Absolute Neutrophil Count
AST	Aspartate Aminotransferase
BARDA	Biomedical Advanced Research and Development Authority
BN	Bavarian Nordic
CDISC	Clinical Data Interchange Standards Consortium
CrCL	Creatinine Clearance
CRA	Clinical Research Associate
CRO	Contract Research Organization
CTS	Clinical Trial Site
CVA	Chorioallantois Vaccinia Virus Ankara
DMID	Division of Microbiology and Infectious Diseases
DS	Drug Safety
DSMB	Data Safety Monitoring Board
ECG	Electrocardiogram
eCRF(s)	Electronic Case Report Form(s)
ELISA	Enzyme-linked Immunosorbent Assay
FAS	Full Analysis Set
FDA	United States Food and Drug Administration
FU	Follow-up
GCP	Good Clinical Practice
GH-RH	Growth Hormone Releasing Hormone
GMP	Good Manufacturing Practice
GMT	Geometric Mean Titer
HBV	Hepatitis-B-Virus
HCG	Human Choriogonadotropin
HCV	Hepatitis-C-Virus
HIPAA	Health Insurance Portability and Accountability Act
HIV	Human Immunodeficiency Virus
ICF	Informed Consent Form
ICH	International Conference of Harmonization of Technical Requirements for Registration of Pharmaceuticals for Human Use
IEC	Independent Ethical Committee
IVRS	Interactive Voice Response System
IWRS	Interactive Web Response System
i.m.	Intramuscular
IND	Investigational New Drug (Application)
IMP	Investigational Medicinal Product

IRB	Institutional Review Board
LLN	Lower Limit of Normal
LV	Left Ventricular
MedDRA	Medical Dictionary for Regulatory Activities
MP	Medical Product
MVA	Modified Vaccinia Ankara Strain
MVA-BN ®	Modified Vaccinia Ankara – Bavarian Nordic
NHP	Non-Human Primates
NIAID	National Institute of Allergy and Infectious Diseases
NIH	National Institutes of Health
NYCBH	New York City Board of Health
ODM	Operational Data Modeling
PEI	Paul Ehrlich Institut
PI	Principal Investigator
PPS	Per Protocol Set
PRNT	Plaque Reduction Neutralization Test
SADR	Serious Adverse Drug Reaction
SAE	Serious Adverse Event
s.c.	Subcutaneous
SCR	Screening Visit
SD	Standard Deviation
TBS	Tris-buffered Saline
TCID 50	Tissue Culture Infectious Dose 50%
ULN	Upper Limit of Normal
US(A)	United States (of America)
V	Visit
VRBPAC	Vaccines and Related Biological Products Advisory Committee
VV	Vaccinia Virus
VV-WR	Vaccinia Virus Western Reserve
WBC	White Blood Cell Count
WHO	World Health Organization
WOCBP	Women of Childbearing Potential

## 1.5 Protocol Synopsis

Title	A randomized, double-blind, placebo-controlled Phase III trial to evaluate immunogenicity and safety of three consecutive production lots of IMVAMUNE ® (MVA-BN ® ) smallpox vaccine in healthy, vaccinia-naïve subjects.
Clinical phase	Phase III
Sponsor	Bavarian Nordic A/S [name] [name], Denmark
Coordinating Investigator	[name] [name]. Division of Infectious Diseases University of Alabama at Birmingham [name] [name] [name], USA
Number of clinical trial sites and country/ies	Up to 40 in the United States of America (USA)
Vaccination dose and schedule	Two vaccinations four weeks apart (at Day 0 and Day 28) with either 0.5 ml IMVAMUNE ® vaccine containing a nominal titer of $1 \times 10^8$ TCID 50 (standard dose) or 0.5 ml placebo (Tris-buffered saline, TBS).
Route of administration	Each IMVAMUNE ® vaccination / placebo administration consists of one subcutaneous (s.c.) injection.
Trial duration	Up to 39 weeks for each subject.
Sample size	4,000 (1,000 subjects per group).

---

Primary objective	To assess the consistency of three consecutively produced IMVAMUNE ® lots.
-------------------	---

---

Secondary objectives	
To assess uncommon adverse reactions, in particular any cardiac sign and symptom indicating a case of myo-/pericarditis, and to compare the frequency of those reactions against placebo.
 
To collect vaccinia-specific humoral immune response data.

----------------------	--

---

Primary endpoint	Geometric Mean Titers (GMTs) after two IMVAMUNE ® vaccinations measured by Plaque Reduction Neutralization Test (PRNT) at trial Visit 4.
------------------	---

---

Secondary endpoints	
Immunogenicity
 
GMTs after two IMVAMUNE® vaccinations measured by Enzyme-linked Immunosorbent Assay (ELISA) at trial Visit 4.
 
PRNT and ELISA seroconversion rates at trial Visit 4.
 
Pearson Correlation Coefficient between the log10 transformed PRNT titers and the log10 transformed ELISA titers at trial Visit 4.
 
Safety and Reactogenicity
 
Occurrence, relationship and intensity of any Serious Adverse Event (SAE) at any time during the trial.
 
Occurrence, relationship and intensity of any cardiac sign or symptom indicating a case of myo-/pericarditis.
 
Occurrence of any Grade 3 or 4 adverse events (AEs) probably, possibly or definitely related to the trial vaccine within 28 days after vaccination.
 
Occurrence, relationship and intensity of unsolicited non-serious AEs within 28 days after each vaccination.
 
Occurrence, intensity and duration of solicited local AEs (redness, swelling, induration, pruritus and pain) during the 8-day period (day of vaccination and the following 7 days) after each vaccination.
 
Occurrence, relationship, intensity and duration of solicited general

---------------------	---

AEs (pyrexia, headache, myalgia, nausea, fatigue and chills) during the 8-day period (day of vaccination and the following 7 days) after each vaccination.

Trial design

Randomized, double-blind, placebo-controlled:

Group 1	1,000 subjects will receive two s.c. vaccinations with 0.5 ml IMVAMUNE ® Lot 1
Group 2	1,000 subjects will receive two s.c. vaccinations with 0.5 ml IMVAMUNE ® Lot 2
Group 3	1,000 subjects will receive two s.c. vaccinations with 0.5 ml IMVAMUNE ® Lot 3
Group 4	1,000 subjects will receive two s.c. vaccinations with 0.5 ml Placebo (TBS)

Visit Schedule:

Visit (V)	Day	Target Week	Vaccination
SCR	Day -28 to -1	-4	
V1	Day 0	0	X
V2	V1 +12 - 16	2	
V3	V1 +28 - 35	4	X
V4	V3 +12 - 16	6	
V5	V3 +28 - 35	8	
Phone FU	V3 +182 - 210	30	

Subject entry criteria

Inclusion criteria

1. Male and female subjects, 18 to 40 years of age
2. The subject has read, signed and dated the informed consent form, having been advised of the risks and benefits of the trial in a language understood by the subject and prior to performance of any trial specific procedures
3. BMI  $\geq$  18.5 and  $<$  35
4. Women of childbearing potential (WOCBP) must have used an acceptable method of contraception for 30 days prior to the first vaccination, must agree to use an acceptable method of contraception during the trial, and must avoid becoming pregnant for at least 28 days after the last vaccination. A woman is considered of childbearing potential unless post-menopausal or

with a history of hysterectomy (Acceptable contraception methods are restricted to abstinence, barrier contraceptives, intrauterine contraceptive devices or licensed hormonal products)

5. WOCBP must have a negative serum pregnancy test at screening and a negative urine pregnancy test within 24 hours prior to each vaccination
6. White blood cells  $\geq 2,500/\text{mm}^3 < \text{ULN}$
7. Absolute neutrophil count (ANC) within normal limits
8. Hemoglobin within normal limits
9. Platelets within normal limits
10. Adequate renal function defined as a calculated Creatinine Clearance (CrCl)  $> 60 \text{ ml/min}$  as estimated by the Cockcroft-Gault equation:
  - For men:  $(140 - \text{age in years}) \times (\text{body weight in kg}) \div (\text{serum creatinine in mg/dl} \times 72) = \text{CrCl (ml/min)}$
  - For women: multiply the result by 0.85 = CrCl (ml/min).
11. Adequate hepatic function defined as:
  - a. Total bilirubin  $\leq 1.5 \times \text{ULN}$  in the absence of other evidence of significant liver disease
  - b. Aspartate aminotransferase (AST), alanine aminotransferase (ALT) and alkaline phosphatase  $\leq 1.5 \times \text{ULN}$
12. Troponin I  $< 2 \times \text{ULN}$
13. Electrocardiogram (ECG) without clinically significant findings (e.g. any kind of atrioventricular or intraventricular conditions or blocks such as complete left or right bundle branch block, AV node block, QTc or PR prolongation, premature atrial contractions or other atrial arrhythmia, sustained ventricular arrhythmia, two premature ventricular contractions in a row, ST elevation consistent with ischemia)

Exclusion criteria

1. Typical vaccinia scar
2. Known or suspected history of smallpox vaccination
3. History of vaccination with any poxvirus-based vaccine
4. US Military service prior to 1991 or after January 2003
5. Pregnant or breast-feeding women

6. Uncontrolled serious infection, i.e. not responding to antimicrobial therapy
7. History of any serious medical condition, which in the opinion of the investigator would compromise the safety of the subject or would limit the subject's ability to complete the trial
8. History of or active autoimmune disease, persons with vitiligo or thyroid disease taking thyroid replacement are not excluded
9. Known or suspected impairment of immunologic function including, but not limited to, HIV Infection, clinically significant liver disease (including chronic active HBV or HCV), diabetes mellitus, moderate to severe kidney impairment
10. History of malignancy other than squamous cell or basal cell skin cancer, unless there has been surgical excision that is considered to have achieved cure. Subjects with history of skin cancer must not be vaccinated at the previous tumor site
11. History or clinical manifestation of clinically significant and severe hematological, pulmonary, central nervous, cardiovascular or gastrointestinal disorders
12. Clinically significant mental disorder not adequately controlled by medical treatment
13. History of coronary heart disease, myocardial infarction, angina pectoris, congestive heart failure, cardiomyopathy, stroke or transient ischemic attack, uncontrolled high blood pressure, or any other heart condition under the care of a doctor
14. Known history of an immediate family member (father, mother, brother, or sister) who has had onset of ischemic heart disease before age 50 years
15. Ten percent or greater risk of developing a myocardial infarction or coronary death within the next 10 years using the National Cholesterol Education Program's risk assessment tool (<http://hin.nhlbi.nih.gov/atpiii/calculator.asp?usertype=prof>)  
NOTE: This criterion applies only to subjects 20 years of age and older
16. Active or history of chronic alcohol abuse and/or intravenous and/or nasal drug abuse (within the past 6 months)
17. Known allergy to IMVAMUNE® vaccine and its constituents, e.g. tris (hydroxymethyl)-amino methane, including know allergy to egg or aminoglycosides
18. History of anaphylaxis or severe allergic reaction to any vaccine
19. Acute disease (illness with or without a fever) at the time

enrollment

20. Body temperature  $\geq 100.4^{\circ}\text{F}$  ( $\geq 38.0^{\circ}\text{C}$ ) at the time of enrollment
  21. Having received any vaccinations or planned vaccinations with a live vaccine within 30 days prior to or after trial vaccination
  22. Having received any vaccinations or planned vaccinations with a killed vaccine within 14 days prior to or after trial vaccination
  23. Chronic systemic administration (defined as more than 14 days) of  $> 5$  mg prednisone (or equivalent)/day or any other immune-modifying drugs during a period starting from three months prior to administration of the vaccine and ending at last physical trial visit (V5)
  24. Post organ transplant subjects whether or not receiving chronic immunosuppressive therapy
  25. Administration or planned administration of immunoglobulins and/or any blood products during a period starting from three months prior to administration of the vaccine and ending at last physical trial visit (V5)
  26. Use of any investigational or non-registered drug or vaccine other than the trial vaccine within 30 days preceding the first dose of the trial vaccine, or planned administration of such a drug during the trial period
  27. Trial personnel
-

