#### Adverse Drug Reactions

Suspected ADRs, i.e. AEs for which there is a reasonable possible relationship to the trial vaccine, were reported in completed clinical trials POX-MVA-001, -002, -004, -005, -007, -008, -009, -010, -011, -023, -024, -028, HIV-NEF-004 and HIV-POL-002 (n = 2901) as following:

Very common (≥ 10%): vaccination site pain, vaccination site erythema, vaccination site swelling, vaccination site induration, vaccination site pruritus, fatigue, myalgia, headache and nausea.

Common (≥ 1% - < 10%): vaccination site warmth, vaccination site hematoma, vaccination site nodule, rigors/chills, increased body temperature, increased troponin I, pyrexia, appetite disorder, arthralgia, pain in extremity and dizziness.

Uncommon ( $\geq 0.1\%$  -  $< 1\%$ ): application site anaesthesia, vaccination site movement impairment, vaccination site discoloration, vaccination site haemorrhage, vaccination site inflammation, vaccination site irritation, paraesthesia, rash, vaccination site reaction, lymphadenopathy, tachycardia, vertigo, conjunctivitis, abdominal pain, diarrhoea, dry mouth, vomiting, asthenia, axillary pain, flushing, malaise, oedema peripheral, influenza, nasopharyngitis, sinusitis, upper respiratory tract infection, contusion, hepatic enzyme increased, white blood cell count decreased, back pain, muscle spasm, muscular weakness, musculoskeletal pain, musculoskeletal stiffness, neck pain, paraesthesia, peripheral sensory neuropathy, sleep disorder, cough, pharyngolaryngeal pain, rhinitis, dermatitis, ecchymosis, hyperhidrosis, night sweats, pruritus, rash, urticaria.

The majority of observed suspected ADRs represented local injection site reactions as well as common systemic reactions, typical for modern injectable vaccines and classified as being mild to moderate. More details on frequencies of suspected ADRs according to System of Organ Class and Preferred Term reported so far in completed IMVAMUNE® clinical trials is provided in the current Investigator's Brochure.

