**Visit 2 (Visit 1 + 12–16 days)**

**The following tasks will be performed:**

- Targeted physical examination including auscultation of the heart and lungs
- Evaluation of vital signs
- Examination of the injection site
- Performing ECG
- Collection of the memory aid handed out at Visit 1, review with subject
- Blood draw for safety laboratory ( 11 ml) including troponin I
- Recording of AEs/SAEs/AESI and concomitant medication

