## 6 Investigational Product

IMVAMUNE® is a highly attenuated live VV (MVA-BN®). It will be provided in liquid-frozen aliquots. One dose of 0.5 ml liquid-frozen vaccine has a nominal virus titer of  $1 \times 10^8$  TCID50 MVA-BN®. IMVAMUNE® will be given s.c.

For further details see current version of the Investigator's Brochure.

Placebo consists of the IMVAMUNE® formulation buffer, TBS. It will be provided in liquid aliquots. One dose of 0.5 ml placebo contains 0.605 mg tris (hydroxymethyl)-amino methane and 4.09 mg sodium chloride.

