### Assessment of Causality

Solicited local AEs are defined as being related to the trial vaccine.

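### The only Grade 3/4 endpoint counts investigator-rated related events, so its comparison with a plain-buffer placebo can be biased by guesses about the arm

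*Protocol*

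**What the plan says.** Protocol section 1.5 lists six safety and reactogenicity endpoints. One concerns Grade 3/4 events: "Occurrence of any Grade 3 or 4 adverse events (AEs) probably, possibly or definitely related to the trial vaccine within 28 days after vaccination". It is the only one of the six that uses relatedness as a condition for being counted. The secondary objective in the same section is to assess uncommon adverse reactions, cardiac ones in particular, and "to compare the frequency of those reactions against placebo". Section 9.5 has summaries shown for each of the four groups and for Groups 1–3 combined, so the vaccine and placebo counts will stand side by side.

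On the comparator, section 6 states: "Placebo consists of the IMVAMUNE ® formulation buffer, TBS". On the vaccine, the adverse drug reaction overview in section 2.6.1 lists as very common (at least 10%) "vaccination site pain, vaccination site erythema, vaccination site swelling, vaccination site induration, vaccination site pruritus, fatigue, myalgia, headache and nausea".

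On who sees what, the Visit 2 and Visit 4 task lists in section 4.2.2 both include "Examination of the injection site", collection and review of the memory aid, and recording of adverse events.

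On causality, section 8.2.5 has unsolicited events rated in five categories, of which possible, probable and definite count as related. Section 8.2.6.2 applies the same rating to solicited general events. Section 8.2.6.1 fixes the local ones by rule: "Solicited local AEs are defined as being related to the trial vaccine".

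**The concern.** A concurrent randomised placebo arm separates vaccine effect from background without anyone judging individual cases. Section 9.3 gives this as the reason for having the arm. Passing events through a causality judgement before comparing arms gives part of that advantage away, unless the judgement is made in ignorance of the arm.

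Ignorance cannot be assumed here. Unblinded preparers are kept away from evaluation (section 6.3), but that does not hide a red or indurated arm, or a diary full of local symptoms. The categories in section 8.2.5 lean on the pharmacological properties of the product, so a belief about which product was given can enter the rating.

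Two things are at stake. The related-only contrast could show an excess on vaccine where the true rates are equal. The endpoint also drops events rated unlikely or none, some of which may be caused by the vaccine. In addition, it combines events that are related by rule (solicited local) with events that are related by judgement (all others), so a difference on the composite is hard to read.

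**Working it through.** **What the plan gives.** It states no rate, power or expected difference for this endpoint. The nearest safety figure is the 95% chance of detecting an event of incidence 1/1,000 among 3,000 vaccinees (section 9.3). It reproduces: 1 − 0.999^3000 = 0.9503. The plan gives only a lower bound for local reactions on vaccine (10%), no rate on placebo, and no attribution shares. Everything below is therefore an assumption, shown as a range, and applies only to events whose relatedness is judged.

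**Step 1: can the arm be guessed?** Allocation is 1:1:1:1, so the prior probability of vaccine is 0.75. With local reaction rates v on vaccine and p on placebo:

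- P(vaccine | reaction) = 0.75v / (0.75v + 0.25p)
- P(placebo | no reaction) = 0.25(1 − p) / [0.25(1 − p) + 0.75(1 − v)]

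| Assumed v / p | P(vaccine given reaction) | P(placebo given none) |
|---|---|---|
| 50% / 10% | 0.375/0.400 = 94% | 0.225/0.600 = 38% |
| 80% / 20% | 0.600/0.650 = 92% | 0.200/0.350 = 57% |
| 90% / 30% | 0.675/0.750 = 90% | 0.175/0.250 = 70% |

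Seeing a reaction is strong evidence of vaccine. Seeing none is weaker evidence of placebo, because three subjects in four receive vaccine.

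**Step 2: what does guessing do to the ratio?** Let h and l be the shares of events called related when vaccine or placebo is believed, and a the probability of guessing correctly, taken as equal in both arms. With equal true event rates the rate cancels:

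ratio = [a·h + (1 − a)·l] / [(1 − a)·h + a·l]

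- h = 40%, l = 20%: a = 0.6 gives 0.32/0.28 = 1.14; 0.7 gives 0.34/0.26 = 1.31; 0.8 gives 0.36/0.24 = 1.50; 0.9 gives 0.38/0.22 = 1.73.
- h = 30%, l = 20%: 0.26/0.24 = 1.08 at a = 0.6, up to 0.29/0.21 = 1.38 at a = 0.9.
- h = 50%, l = 10%: 0.34/0.26 = 1.31 up to 0.46/0.14 = 3.29.

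The all-causality ratio is 1.0 throughout, because h and l do not enter it.

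**Step 3: relax equal accuracy.** Take an assessor who always picks the likelier arm from step 1, with h = 40% and l = 20%.

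- 80%/20%: a reaction means vaccine, none means placebo, so accuracy is 80% in both arms and the ratio is 1.50.
- 90%/30%: accuracy is 90% on vaccine and 70% on placebo. Ratio = (0.9×0.4 + 0.1×0.2) / (0.3×0.4 + 0.7×0.2) = 0.38/0.26 = 1.46.
- 50%/10%: even without a reaction vaccine is likelier (62%), so vaccine is guessed for everyone and the ratio is 0.40/0.40 = 1.0.

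The size of the bias, and under some inputs whether there is any, depends on rates the protocol does not state.

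**Step 4: chance of a nominally significant difference.** This uses 3,000 v 1,000 subjects, a two-sided 5% level, no true difference, and shares called related that differ by actual arm:

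| All-cause rate | 30% v 20% (ratio 1.5) | 40% v 20% (2.0) | 50% v 10% (5.0) |
|---|---|---|---|
| 2% | 9% | 22% | 76% |
| 5% | 19% | 56% | >99% |
| 10% | 38% | 89% | about 100% |

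With equal shares (30% v 30%) the related-only ratio is 1.0 and the rate is the nominal 5%. An all-causality count keeps the nominal 5% whatever the shares.

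**The case against.** **Stronger readings that the protocol does not support**

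- A reader might infer that the trial's whole safety comparison with placebo rests on guesses. It does not. The other five safety endpoints in section 1.5 count occurrence with no relatedness filter, and section 8.1.3.1 requires all events up to Visit 5 to be recorded whatever their causality. An event rated unlikely leaves this endpoint but remains in the data and in another endpoint.
- A reader might infer that the cardiac comparison has the same flaw. It does not. Its endpoint is any cardiac sign or symptom indicating myo-/pericarditis, with relationship recorded but not used as a filter. Section 9.3 compares case incidence, Appendix II supplies case definitions, and ECGs are read centrally.
- A reader might infer that bias is shown. Only a route to it is shown. The ratios rest on assumed inputs, and step 3 includes a case with none.

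**Other points in the plan's favour**

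- Section 9.5 calls secondary tests descriptive, and section 9.3 develops the placebo comparison only for myo-/pericarditis and other cardiac events. This stands and limits the weight of the point, although lack of a formal claim does not remove bias from a reported contrast.
- Solicited local events are related by rule in every arm, and events without a rating become possible in every arm. Neither part is open to guessing. Section 8.2.5 also allows a rating of possible when no other cause is known, even without pharmacological support. All of this dilutes the effect without removing it for the remaining events.
- The listed order of tasks is weak evidence. At Visit 2 adverse event recording comes after diary review, but at Visit 4 it comes before. Injection-site examination precedes it at both visits.
- Table layout belongs to the SAP. That is so, but the endpoint definition is fixed in section 1.5, and the only Grade 3/4 endpoint named there is the filtered one.

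**Conclusion.** The point holds for this one endpoint. For unsolicited and solicited general Grade 3/4 events, inclusion depends on a judgement made at a site that can often see evidence of the arm, so the Groups 1–3 v Group 4 contrast can be biased. The protocol does not determine the size. Across the assumed inputs in steps 2 and 3, the related-only ratio under no true difference runs from 1.0 to 3.29, and from 1.14 to 1.73 in the middle case with 60% to 90% correct guessing. These figures assume that attribution follows belief about the arm, and most also assume equal guess accuracy in both arms. No confirmatory conclusion depends on the endpoint. It is a worthwhile and inexpensive improvement rather than a threat to the trial.

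**What to change.** In section 1.5, add as an endpoint the occurrence of any Grade 3 or 4 adverse event within 28 days after each vaccination regardless of relationship, and name it as the basis for comparing Groups 1–3 combined with Group 4. Keep the related-only count as supportive, with solicited local events shown separately because their relatedness is set by definition. The cardiac endpoint needs no change.

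The cost is a wording change and one extra table set. The data are already collected. Reported Grade 3/4 percentages will be higher in both arms because background events are included.
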